11.4.1 Analysis Populations

11.4.1.1 Safety Population

The Safety Population will consist of all subjects who have received the study vaccine and for whom any data on safety are available. Subjects will be classified according to the treatment received. The primary safety analysis will be done on this population.

11.4.1.2 Immunogenicity Population

The Immunogenicity Population will include all subjects who have received the study vaccination and contributed both pre-vaccination samples and either at least one post vaccination sample for humoral immunogenicity testing for which valid results were reported, or at least one post vaccination nasal sample for which valid results were reported. Subjects will be classified according to the treatment received.

11.4.1.3 Per Protocol Population

The Per Protocol (PP) Population will include all subjects in the immunogenicity population, with the following exclusions:

- Data from all available visits for subjects found to be ineligible at baseline.
- Data from all visits subsequent to major protocol deviations, such as:
 - Receipt of non-study licensed live vaccine within 30 days before or after the study vaccination,
 - Receipt of non-study licensed inactivated vaccine within 14 days before or after the study vaccination,
 - Receipt of immunosuppressive therapy (e.g., corticosteroids) within 30 days before or after the study vaccination.

-
- Data from any visit that occurs substantially out of window. Whether a visit that occurs substantially out of window will be determined jointly by the principal investigator, the Sponsor, and the DCC.

For analyses using the PP population, subjects will be grouped based on study vaccinations received.

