11.4 Final Analysis Plan

The results obtained from this study will be used to inform the dose recommended for a subsequent Phase 2b study. Clinical, safety, reactogenicity, immunogenicity and *B. pertussis* colonization data through approximately 45 days after study vaccination, or 28 days after study vaccination if no subjects remain colonized with *B. pertussis* at Day 29, will represent the primary clinical database for this trial. Once the last subject completes the visit that occurs approximately 45 days after study vaccination (or approximately 28 days after study vaccination, if no subjects remain colonized with *B. pertussis* at the Day 29 visit), the primary clinical database will be cleaned, monitored, and frozen. Analyses of safety, reactogenicity, immunogenicity, and *B. pertussis* colonization data by treatment arm are planned, including descriptive summaries of 15-day reactogenicity data, 28-day adverse event data (including SAE, NOCMC and AESI), 28 and 45-day nasal clearance data, and humoral and mucosal immunogenicity data through Day 46 (or Day 29 if no subjects remain colonized with *B. pertussis* at the Day 29 visit). As it is anticipated that subjects will remain in long term immunogenicity and safety follow-up at the time of these analyses, the presentation of these data will not include any unblinded listings of individual subject data and aggregate summaries will be in a format that prevents inadvertent unblinding of the sponsor or clinical investigators to any individual subject's treatment assignment or immune response data.

A preliminary report will be prepared by the DCC after the primary clinical database is cleaned, monitored, and frozen and all immunogenicity and colonization data through Day 46 (or Day 29 if no subjects remain colonized with *B. pertussis* at the Day 29 visit) are received. These analyses may be made available to DMID and the vaccine company partner and to the lead principal investigator for planning subsequent trials. These analyses will not be used to make any decisions concerning the conduct of this trial. A formal statistical analysis plan that defines the analyses of data to be included in the preliminary report for early release and the CSR will be developed and finalized prior to the to the Day 46 data freeze (or Day 29 if no subjects remain colonized with *B. pertussis* at the Day 29 visit).

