Analysis of Day 181 humoral and mucosal immunogenicity data may be performed and released as the data are available from the research laboratories. Any such analyses would be considered the final analysis for the endpoint, and included in the CSR.

Once the last subject completes the last visit, the final clinical database will be cleaned, monitored and locked. Unblinded analyses of safety, reactogenicity, colonization, and available immunogenicity data will then be performed by the DCC and will be included in the CSR. All safety analyses will be performed using the safety population, all immunogenicity analyses will be performed using the immunogenicity and the per-protocol (PP) populations, whereas all

colonization data will be summarized using per-protocol population. The analysis populations are defined below ([Section 11.4.1.](#))

All analyses will be presented by treatment group (i.e. group by BPZE1 10^9 CFU, BPZE1 10^7 CFU, or Placebo). In addition, results for BPZE1 at dose of 10^9 CFU will be further grouped by vaccination device (group by VaxINator or needleless tuberculin syringe) to allow for comparison of immunogenicity results with previous results from Phase 1 clinical trials of BPZE1 (these previous trials used needleless tuberculin syringe as device for administration).

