6.3.3. Per Protocol Population

The Per Protocol (PP) Population will include all subjects in the immunogenicity population, with the following exclusions:

-
- Data from all available visits for subjects found to be ineligible at baseline.
 - Data from all visits subsequent to major protocol deviations, such as:
 - Receipt of non-study licensed live vaccine within 30 days before or after the study vaccination,
 - Receipt of non-study licensed inactivated vaccine within 14 days before or after the study vaccination,
 - Receipt of immunosuppressive therapy (e.g., corticosteroids) within 30 days before or after the study vaccination.
 - Data from any visit that occurs substantially out of window. Whether a visit that occurs substantially out of window will be determined jointly by the principal investigator, the Sponsor, and the SDCC.

For analyses using the PP population, subjects will be grouped based on study vaccinations received.

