7.2. Protocol Deviations

A summary of subject-specific protocol deviations will be presented by the deviation category, deviation type, and treatment group for all enrolled subjects ([Table 5](#).) Deviations that are considered major deviations that will be reviewed for possible subject exclusion from the per protocol population include: deviations related to eligibility/enrollment, treatment administration schedule, follow-up visit schedule, and study product or specimen temperature excursions. All subject-specific protocol deviations and non-subject specific protocol deviations will be included in [Appendix 3](#) as data listings ([Listing 2](#) and [Listing 3](#), respectively.)

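### Per-protocol exclusion of out-of-window visits has no limit in days, decision date, blinding or lock, and colonisation is tabulated only in that population

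*Protocol*

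**What the plan says.** Protocol 11.4.1.3 removes from the per-protocol set "Data from any visit that occurs substantially out of window", and on who decides it says "Whether a visit that occurs substantially out of window will be determined jointly by the principal investigator, the Sponsor, and the DCC". SAP 6.3.3 keeps the rule: the question "will be determined jointly by the principal investigator, the Sponsor, and the SDCC". SAP 7.2 comes closest to a process: "Deviations that are considered major deviations that will be reviewed for possible subject exclusion from the per protocol population include" four categories, one of which is the follow-up visit schedule. It does not say when the review takes place or what the reviewers may know.

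Protocol 11.4 plans a preliminary analysis through Day 46 (Day 29 if nobody remains colonised). It covers safety, reactogenicity, immunogenicity and "colonization data by treatment arm are planned, including descriptive summaries of 15-day reactogenicity data". On its release the protocol says "These analyses may be made available to DMID and the vaccine company partner and to the lead principal investigator". Protocol 15.4 is firmer and says that they will be. Day 181 follow-up is expected to be still running at that point.

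The populations differ by endpoint. Serum and mucosal immunogenicity is reported in both the Immunogenicity and per-protocol populations (Protocol 11.4.3, SAP 8.1). For the culture endpoint, Protocol 11.4 says that all "colonization data will be summarized using per-protocol population". Protocol 11.4.2, SAP 6.3, SAP 8.1 and SAP Table 33 agree.

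**The concern.** An exclusion rule protects an analysis only if it is fixed before anyone who applies it can know which way an exclusion would push the result. Here the criterion is a matter of judgement, and nothing says when that judgement is made, what the deciders may have seen, or that a decision once made stands.

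Two outcomes are exposed, by different routes. Day 181 per-protocol immunogenicity is judged after by-arm results can have gone to two of the three deciders. Day 29 and Day 46 colonisation is judged by a group that includes the investigator, whose site holds individual culture results. Colonisation is a named secondary outcome for a live vaccine. The trial is meant to inform the Phase 2b dose (Protocol 11.4), and the arms have 15 or 5 subjects, so one visit matters.

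**Working it through.** **1. Is the gap closed anywhere?** Compared on what a pre-specified rule needs:

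| Element | Protocol 11.4.1.3 | SAP 6.3.3 | SAP 7.2 |
|---|---|---|---|
| Days beyond window | none | none | none |
| Decision date | none | none | none |
| Blind to arm or results | not stated | not stated | not stated |
| Lock on decisions | none | none | none |
| Deciders | investigator, Sponsor, DCC | investigator, Sponsor, SDCC | not named |

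The SAP was due before the Day 46 freeze (Protocol 11.4), so it was the natural place to settle this. The visit windows themselves are numeric (Protocol 7.3 and 7.4): Day 15 ± 3, Day 29 ± 3, Day 46 ± 3 and Day 181 ± 21. Only the margin that makes a visit *substantially* late or early is missing.

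**2. Who knows what, and when?**
- Through Day 46: the per-protocol tables, including Table 33, carry the asterisk that places them in the Preliminary Report (SAP Appendix 1). Membership for those visits must therefore be set before the report exists, and the first decisions come before the by-arm release.
- Day 181: these visits and assays follow the release, so their per-protocol status can be decided by people who have seen by-arm Day 15 and Day 29 results.
- Culture results: Visit 4a takes place only if the Day 29 culture is positive (Protocol 7.3.4, Appendix A), so the site learns each result. Protocol 3.2.2 attributes any positive to the study product. This route does not depend on the preliminary report.
- The DCC: its statisticians prepare the randomization code (Protocol 5.3.1), and it prepares the preliminary report. It is a third party, but it is not described as a blinded one.

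**3. How much can one visit move colonisation?** The point rests on no figure in the plan, so there is none to reproduce. Arm sizes of 15 and 5 come from Protocol Table 2. The number of positives is assumed. The plan does not name the interval method for colonisation; exact Clopper-Pearson limits are assumed here. For x positives of n, the lower limit is the 0.025 quantile of Beta(x, n − x + 1) and the upper limit is the 0.975 quantile of Beta(x + 1, n − x). When x = 0 the lower limit is 0 and the upper limit is 1 − 0.025^(1/n).

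| Arm | All cultures | One positive visit excluded |
|---|---|---|
| 15 subjects | 1/15 = 6.7% (0.2 to 31.9) | 0/14 = 0% (0 to 23.2) |
| 5 subjects (syringe) | 1/5 = 20.0% (0.5 to 71.6) | 0/4 = 0% (0 to 60.2) |

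For 0/14 the upper limit is 1 − 0.025^(1/14) = 0.232. For 0/4 it is 1 − 0.025^(1/4) = 0.602. One exclusion turns some persistence at Day 29 into none observed, and in the 15-subject arm it lowers the upper limit by 31.9 − 23.2 = 8.7 percentage points.

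**The case against.** Several safeguards are real.

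- The preliminary report has no unblinded individual listings, and its format must protect individual assignments and immune responses (Protocol 11.4). Site unmasking waits until after the CSR, and assay staff are blinded (Protocol 5.3.2). An arm-level summary does not show whether a given late Day 181 visit belongs to a responder, or to which arm.
- The Immunogenicity Population has no window rule and is tabulated beside the per-protocol set. SAP 6.3 even makes the per-protocol immunogenicity analysis optional, which sits badly with SAP 8.1. A selective exclusion would appear as a gap between paired tables.
- Exclusions are listed in the CSR (Listing 4), as are individual culture results (Listing 13).
- Discretion reaches only visits that are actually out of window, and the decision is joint.

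All of this stands, and it confines the immunogenicity risk to a supportive analysis. It does less for colonisation, which has no paired table, and neither listing is in the Preliminary Report. A listing also shows what was dropped without making the choice prospective.

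Two stronger readings are tempting. The first is that people who have seen the by-arm results choose whose colonisation data count. The documents do not support this: the first Day 29 and Day 46 decisions precede the report, the data are to be frozen, and no section provides for reopening membership, although none forbids it.

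The second is that one exclusion decides significance. Near-boundary counts can be found: 7/15 v 2/15 gives a pooled Barnard p of 0.055, and 7/14 v 2/15 gives 0.035. But those counts are invented. At 11/15 v 1/15, dropping a responder moves p only from 0.0001 to 0.0003. The plan disclaims formal testing (Protocol 11.1, SAP 8.1), and no p-value is planned for colonisation.

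**Conclusion.** The point holds in a limited form. The exclusion rule is discretionary, undated, not required to be blind and not locked, in both documents. For Day 181 immunogenicity the consequence is confined to a supportive per-protocol analysis, because the preliminary results are aggregate and the Immunogenicity Population is shown alongside. For colonisation the consequence is more direct: the only summary table can lose a positive subject through a judgement made at a site that knows the culture result.

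The illustrated size, 6.7% to 0% in a 15-subject arm or 20% to 0% in the syringe arm, assumes one positive subject per arm whose Day 29 visit was out of window, and exact intervals. Nothing in the documents suggests that such an exclusion was intended. Severity is minor to moderate.

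**What to change.** 1. In SAP 6.3.3, replace the case-by-case judgement with a limit in days for each visit: either the protocol windows or a stated margin beyond them. The windows alone would be stricter than the present wording, so the choice should be explicit.
2. Record and lock per-protocol membership for visits through Day 46 before the primary freeze, by people blind to arm, culture and assay results. Apply the same numeric rule to Day 181 before Day 181 assay data are merged.
3. Beside Table 33, add a colonisation table for all vaccinated subjects with a culture result, showing the number tested at each time point.

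The cost is a few lines of SAP text and one table shell, with no new data. The downside is that a fixed limit may drop a slightly late visit from the per-protocol set. The Immunogenicity Population and the added table would retain it.

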11.4.2 Safety Data

Summaries and analysis of safety data will be presented for the Safety Analysis Population. All summaries and analyses will be presented by treatment group.

Solicited AEs will be summarized by severity for each day after the study vaccination (Days 1-14 post study vaccination) and as the maximum severity over all 15 days. Additionally, solicited AEs will be analyzed by taking the most severe response over the follow-up period, dichotomizing into a binary variable (none versus mild, moderate, or severe) and using standard techniques, such as exact confidence intervals, to summarize the proportion of subjects reporting each symptom, any local symptom, and any systemic symptom. Summaries of solicited AEs will be presented separately for each study vaccination as well as overall study vaccinations by treatment arm. The proportion of subjects reporting symptoms may be compared between treatment arms using Chi-square or Fisher's exact test.

Unsolicited AEs will be coded by Medical Dictionary for Regulatory Activities (MedDRA[®]) for preferred term and system organ class (SOC). SAEs will be reported by detailed listings showing the event description, MedDRA[®] preferred term and SOC, relevant dates (study vaccinations and AEs), severity, relatedness, and outcome for each event. Non-serious unsolicited AEs will be summarized as number and percentage of subjects reporting at least one event in each MedDRA[®] preferred term and SOC, cross tabulated by severity and relationship to study product. Additionally, the proportion of subjects and exact 95% confidence intervals of AEs in aggregate and by MedDRA[®] categories will be computed.

Subjects will be tested for *B. pertussis* colonization by culture at Day 29 and, if positive, again at Day 46. The proportion of subjects with positive *B. pertussis* culture will be reported for the PP population at each time point with corresponding 95% confidence intervals.

11.4.3 Immunogenicity Data

Summaries and analysis of immunogenicity data will be presented for the immunogenicity and PP populations by treatment group.

Immune responses in terms of toxin-specific serum IgG and IgA antibody titers (PT, FHA, PRN, FIM 2/3) will be summarized at each time point. Analyses will include the Geometric Mean Titers (GMTs) along with corresponding 95% confidence intervals and Geometric Mean Fold Rise (GMFR), as well as the proportion of subjects achieving seroconversion (defined as 2-fold increase over baseline of GMT) for each antigen (PT, FHA, PRN, and FIM 2/3) and the proportion of subjects that achieved seroconversion for ≥ 1 and ≥ 2 antigens (PT, FHA, PRN, and FIM 2/3).

Immune responses in terms of the ratio of toxin-specific (PT, FHA, PRN, FIM 2/3) nasal mucosal IgA antibody to total nasal mucosal IgA antibody will be summarized at each time point. Analyses will include the geometric mean titer ratios (GMTR) of antigen-specific IgA to total IgA and corresponding 95% confidence intervals, along with fold change of the GMTR from baseline. The proportion of subjects achieving seroconversion, defined as ≥ 2 -fold rise of the GMTR from baseline, to each antigen (PT, FHA, PRN, and FIM 2/3) will be reported as well as the proportion of subjects that achieve seroconversion by nasal aspirate ELISA to one or more antigens (PT, FHA, PRN, and FIM 2/3) at either or both of Day 29 and Day 181.

11.4.4 Missing Values and Outliers

All attempts will be made to collect all data per protocol. As missing data are expected to be minimal, no imputation will be performed for missing values. Any data point that appears to be erroneous or inexplicable based on clinical judgment will be investigated as a possible outlier. If data points are identified as outliers, sensitivity analyses will be performed to examine the impact of including or excluding the outliers. Any substantive differences in these analyses will be reported.

12 SOURCE DOCUMENTS AND ACCESS TO SOURCE DATA/DOCUMENTS

The participating VTEU site will maintain appropriate medical and research records for this study, in compliance with ICH E6, Section 4.9, and regulatory and institutional requirements for the protection of confidentiality of subjects. The participating VTEU site will permit authorized representatives of the DMID, its designees, and appropriate regulatory agencies to examine (and when required by applicable law, to copy) clinical study records for the purposes of quality assurance reviews, audits, monitoring and evaluation of the study safety and progress. These representatives will be permitted access to all source data, which include, but are not limited to, hospital records, clinical and office charts, laboratory notes, memoranda, evaluation checklists, pharmacy dispensing records, recorded data from automated instruments, copies or transcriptions certified after verification as being accurate and complete, microfiches, photographic negatives, microfilm or magnetic media, x-rays, and subject files and records kept at the pharmacy, at the laboratories, and medico-technical departments involved in the study. Source data are all information, original records of clinical findings, observations, or other activities in a clinical study necessary for the reconstruction and evaluation of the study. Interview of subjects is sufficient for obtaining medical history. Solicitation of medical records from the subject's primary care provider is not required unless needed.

13 QUALITY CONTROL AND QUALITY ASSURANCE

Following a written DMID-accepted site quality management plan, the participating VTEU site is responsible for conducting routine quality assurance (QA) and quality control (QC) activities to internally monitor study progress and protocol compliance. The site principal investigators will provide direct access to all study-related sites, source data/data collection forms, and reports for monitoring and auditing by the sponsor, and inspection by local and regulatory authorities. The site principal investigators will ensure all study personnel are appropriately trained and applicable documentations are maintained on site. The DCC will implement quality control procedures beginning with the data entry system and generate data quality control checks that will be run on the database. Any missing data or data anomalies will be communicated to the participating VTEU site for clarification and resolution.

DMID-designated clinical monitors will verify that the clinical trial is conducted and data are generated, documented (recorded), and reported in compliance with the protocol, ICH/GCP guidelines, and the applicable regulatory requirements. Clinical monitoring reports will be submitted to DMID.

14 ETHICS/PROTECTION OF HUMAN SUBJECTS

14.1 Ethical Standard

The site's principal investigator will obtain IRB approval for this protocol to be conducted at the research site and send supporting documentation to the DMID before initiating recruitment of subjects. The investigator will submit applicable information to the IRB on which it relies for the review, to conduct the review in accordance with 45 CFR 46, ICH E6 GCP, and as applicable, 21 CFR 56 (Institutional Review Boards) and 21 CFR 50 (Protection of Human Subjects), other federal, state, and local regulations. The IRB must be registered with OHRP as applicable to the research. DMID must receive the documentation that verifies IRB-approval for this protocol, associated informed consent documents, and upon request any recruitment material and handouts or surveys intended for the subjects, prior to the recruitment and enrollment of subjects.

Any amendments to the protocol or consent materials will be approved by the IRB before they are implemented. IRB review and approval will occur at least annually throughout the enrollment and follow-up of subjects, and may cease if annual review is no longer required by applicable regulations. The investigator will notify the IRB of deviations from the protocol and reportable SAEs, as applicable to the IRB policy.

Each institution engaged in this research will hold a current Federalwide Assurance (FWA) issued by the Office of Human Research Protection (OHRP) for federally funded research.

